8.1.4. Subgroup Analyses

Subgroup analyses, using descriptive statistics only, will be performed on the US/FDA primary efficacy endpoint for the ITT population at Month 6. Analyses will be performed to determine the treatment effect within specific subgroups of interest, and to determine if the treatment effect

¹ These analyses respond to guidance received from FDA in its correspondence to pSivida dated September 22, 2015.

is consistent across different subgroup levels. Subgroups will be defined on the basis of study eye baseline characteristics, including:

- Severity of macular edema [CSFT < 300 microns, CSFT >= 300 microns]
- Duration of disease [< 2 years, 2 to 5 years, > 5 years]
- Lens status [Phakic, Aphakic, Pseudophakic]
- Intraocular pressure [10 to 15 mmHg, >15 to 21 mmHg]
- History of incisional surgery to control elevated IOP [History, No History]
- Presence/absence of vitrectomy
- BCVA [<= 49 letters, > 49 letters]
- Randomization strata [Not receiving systemic treatment, Receiving systemic treatment – corticosteroid therapy, Receiving systemic treatment – immunosuppressive therapy]

Subgroup analyses will also be performed based on region [US, EMEA, India].

Additionally, subgroups will be defined based on IOP lowering medication or surgery received in the study eye, as follows:

- Use of IOP lowering medication [No IOP lowering medication, Required IOP lowering medication]
- Surgical Intervention to Control Elevated IOP [No surgical intervention, Required surgical intervention]

IOP lowering medication status will be based on a subject's use of any IOP lowering medication in the study eye up to the time point of interest (Month 6, 12 or 36). Surgical intervention status will be defined in a similar manner.

8.2. Exploratory Efficacy Endpoints

The proportion of subjects with recurrence in the study eye within 12 and 36 months will be analyzed using the same inferential analysis employing the same methods as for the primary analysis as noted in [Section 8.1.1](#). Sensitivity analysis will also be performed for the proportion of subjects with recurrence in the study eye within 12 and 36 months as noted in [section 8.1.3](#).

The following endpoints will be analyzed for the ITT and PP populations employing descriptive statistics only:

- Proportion of subjects in each treatment group who have a recurrence of uveitis in the fellow eye (within 6 months, within 12 months and within 36 months)
- Mean change from baseline in BCVA letter score in the study eye in each treatment group (at 6 months, 12 months and 36 months)
- Number of recurrences of uveitis in each treatment group (within 6 months, within 12 months and within 36 months)
- Time to recurrence of uveitis in study eye in each treatment group (within 6 months, within 12 months and within 36 months)
- Number of adjunctive treatments required to treat recurrences of uveitis in each treatment group (within 6 months, within 12 months and within 36 months)

- Resolution of macular edema, as measured by OCT imaging (at 6 months, 12 months and 36 months)

Exploratory analyses will use the US/FDA definition of recurrence of uveitis. No missing data will be imputed other than as noted in [Section 8.1.2](#). The data imputation method will be applied to recurrence of uveitis in the fellow eye values in the same manner as the study eye, with the 3rd criteria revised to consider use of prohibited local medications in the fellow eye, instead of the study eye.

The number and percentage of subjects with a recurrence of uveitis in the study eye within 12 months and within 36 months and with a recurrence of uveitis in the fellow eye within 6 months, within 12 months and within 36 months will be presented by treatment group.

ETDRS letter score absolute value and change from baseline at Month 6 (and 12 and 36) will be described for each treatment group using descriptive statistics.

For each subject and eye (study, fellow), the number of recurrences through Month 6, 12 and 36 will be calculated. Recurrences imputed at Month 6, 12 or 36 due to missing data as per [Section 8.1.2](#) will be considered a recurrence for this calculation. The number of recurrences per subject and eye (study, fellow) will be described using descriptive statistics as well as the number and percentage of subjects by category (0, 1, 2, 3, 4, 5, >5). Additionally the total number of recurrences summed across all subjects, all study eyes and all fellow eyes will be presented by treatment group.

The time to first recurrence of uveitis within 6 months is calculated as the number of days between the date of injection (Day 1) and the visit date of the first reported recurrence of uveitis in the study eye. Subjects who do not experience a recurrence of uveitis within 6 months will be censored at the date of their Month 6 visit. The time to first recurrence of uveitis within 12 (or 36) months will be calculated in a similar manner, censoring at the date of a subject's Month 12 (or 36) visit if the subject does not experience a recurrence of uveitis within 12 (or 36) months. Recurrences imputed at Month 6 (or Month 12 or Month 36) due to missing data as per [Section 8.1.2](#) will be considered a recurrence in the time to recurrence analysis. Median time to recurrence and the 95% confidence interval for the median will be summarized by treatment group and randomization strata. The Kaplan-Meier estimated probabilities of recurrence will also be presented for monthly intervals through 36 months. Since time to recurrence is calculated in days, the monthly intervals will be defined based on 30 days = 1 month. Kaplan-Meier plots for time to first recurrence of uveitis will also be presented.

The number of adjunctive treatments, including systemic steroids or immunosuppressants, intra/peri-ocular steroids, and topical steroids, will be determined using medications/therapies recorded on the Concomitant Medications page with start/end dates within the given time period (6, 12 or 36 months). The number and percentage of subjects by number of adjunctive treatments will be presented by treatment group and category of adjunctive treatment. The intra/peri-ocular steroids and topical steroids will also be presented by eye (study, fellow). Multiple doses of the same medication which are part of one treatment regimen will be counted as one adjunctive treatment for the purposes of analysis.

Resolution of macular edema will be summarized using a shift table comparing the presence (Yes, No, Not Evaluable) of macular edema at Month 6 (and 12 and 36) to the baseline response by eye (study, fellow) and treatment group.

9. Safety Analysis

Safety analyses will be performed on the Safety population at 6, 12 and 36 months. Subjects who are randomized but do not receive treatment will not be included in safety tabulations but have all safety data listed only. Percentages for safety summaries based on the number of subjects with a given event or attribute will be based on the number of subjects who were treated (including sham treatment).

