Diagnosis and Main Criteria for Inclusion: Diagnosis: Unilateral or bilateral chronic non-infectious uveitis affecting the posterior segment of the eye Inclusion Criteria: 
 • Male or non-pregnant female at least 18 years of age at time of consent • One or both eyes having a history of recurrent non-infectious uveitis affecting the posterior segment of the eye with or without anterior uveitis ≥ 1 year duration • During the 12 months prior to enrollment (Day 1), the study eye has either received treatment: 
 • systemic corticosteroid or other systemic therapies given for at least 3 months, and/or • at least 2 intra- or peri-ocular administrations of corticosteroid for management of uveitis OR the study eye has experienced recurrence: 
 • at least 2 separate recurrences of uveitis requiring systemic, intra- or peri-ocular injection of corticosteroid • At the time of enrollment (Day 1), study eye has < 10 anterior chamber cells/HPF and a vitreous haze \leq grade 2. • Visual acuity of study eye is at least 15 letters on the ETDRS chart • Subject is not planning to undergo elective ocular surgery during the study • Subject has ability to understand and sign the Informed Consent Form • Subject is willing and able to comply with scheduled visits, treatment plan, laboratory tests and other study procedures 		

Exclusion Criteria:

- Allergy to fluocinolone acetonide or any component of the FAI insert
- History of posterior uveitis only that is not accompanied by vitritis or macular edema
- History of iritis only and no vitreous cells, anterior chamber cells or vitreous haze
- Uveitis with infectious etiology
- Vitreous hemorrhage
- Intraocular inflammation associated with a condition other than noninfectious uveitis (e.g. intraocular lymphoma)
- Ocular malignancy in either eye, including choroidal melanoma
- Toxoplasmosis scar in study eye or scar related to previous viral retinitis
- Previous viral retinitis
- Current viral diseases of the cornea and conjunctiva including epithelial herpes simplex keratitis (dendritic keratitis), vaccinia, and varicella, mycobacterial infections of the eye or fungal diseases of ocular structures
- Media opacity precluding evaluation of retina and vitreous
- Peripheral retinal detachment in area of insertion

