8. SELECTION AND WITHDRAWAL OF SUBJECTS

8.1. Subject Inclusion Criteria

- Male or non-pregnant female at least 18 years of age at time of consent
- One or both eyes having a history of recurrent non-infectious uveitis affecting the posterior segment of the eye with or without anterior uveitis ≥ 1 year duration.
- During the 12 months prior to enrollment (Day 1),
the study eye has either received treatment:
 - systemic corticosteroid or other systemic therapies given for at least 3 months, and/or
 - at least 2 intra- or peri-ocular injections of corticosteroid for management of uveitis
- OR the study eye has experienced recurrence:
 - at least 2 separate recurrences of uveitis requiring systemic, intra- or peri-ocular injection of corticosteroid
- At the time of enrollment (Day 1), study eye has < 10 anterior chamber cells/HPF and a vitreous haze \leq grade 2.
- Visual acuity of study eye is at least 15 letters on the ETDRS chart
- Subject is not planning to undergo elective ocular surgery during the study
- Subject has ability to understand and sign the Informed Consent Form
- Subject is willing and able to comply with scheduled visits, treatment plan, laboratory tests, and other study procedures

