9.7. Procedures on Day of Treatment

9.7.1. Designation of Study Eye and Randomization

For subjects with unilateral uveitis, the study eye will be the affected eye. For subjects with bilateral uveitis, the study eye will be the worse eye meeting the inclusion/exclusion criteria. For subjects with symmetrical uveitis the study eye will be the right eye. The non-study eye may receive any local ocular treatment at the discretion of the investigator.

If the subject meets the inclusion and exclusion criteria at Screening and Day 1, the randomization to the FAI insert or sham injection will be performed via the IVRS.

Randomization will be stratified on the basis of whether the patient is receiving systemic treatment to control uveitis at the time of study entry. For patients receiving systemic treatment at time of study entry, randomization will be stratified on the basis of the type of treatment (steroid or immunosuppressant).

To preserve study masking as much as possible within the imposed ethical constraints, the study personnel who administer the assigned treatment will refrain from performing any subject assessments after study Day 1. Treatment assignments will be masked to the subjects and to those involved in administering routine follow-up care to the subjects. Follow-up assessments will only be performed by study personnel at the site who are masked to the assigned treatment.

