4.3. Analysis Population

4.3.1. Intent-to-Treat (ITT)

The ITT population will include all randomized subjects. The ITT population will be used for the primary efficacy analysis and all efficacy endpoints.

All subjects in the ITT population will be analyzed according to the treatment they were randomized to receive and not according to what they actually received, in the event there is a discrepancy. Similarly, in any ITT analysis by systemic treatment at study entry (randomization stratification factor), subjects will be analyzed by the strata to which they were randomized, not the actual strata, in the event there is a discrepancy.

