The prohibited medication data (based on preferred terms and/or ATC codes) will be reviewed and medications will be categorized as either having a potential impact on the efficacy assessments (consistent with the US/FDA definition of the primary endpoint) or no impact on the efficacy assessments. Only prohibited medications determined to have a potential impact on efficacy assessments will be taken into consideration for data imputation. The list of prohibited medications which will result in an imputed recurrence of uveitis value, for either eye, will be identified prior to each database lock. Note: although local medications are permitted in the fellow eye, in order to ensure consistency in analysis between the study eye and fellow eye, the same list of medications prohibited in the study eye, including local medications, will be considered “prohibited” for the fellow eye for the purposes of recurrence imputation.

A listing of subjects with missing recurrence information at Month 6 (or Month 12 or Month 36 for the Month 12 or 36 analyses, respectively) will be provided. All available recurrence data for these subjects will be included in the listing.

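### Fellow-eye recurrence is imputed in all randomized subjects, including those whose fellow eye has no uveitis, and from local treatment the protocol permits; this inflates an exploratory endpoint

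*SAP*

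**What the plan says.** **Who is counted.** The diagnosis in the protocol synopsis is "Unilateral or bilateral chronic non-infectious uveitis affecting the posterior segment of the eye", and Protocol 8.1 asks for "One or both eyes having a history of recurrent non-infectious uveitis". One affected eye is therefore enough. SAP 4.3.1 says "The ITT population will include all randomized subjects". SAP 8.2 reports the fellow-eye proportion on the ITT and PP populations and does not restrict it to bilateral disease. The default denominator in SAP 4 is every subject in the arm within the analysis population.

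**What is imputed.** SAP 8.1.2 scores a recurrence, in a subject without an earlier one, for a missing required examination at the analysis visit, for a prohibited systemic drug, or for a prohibited local drug in the study eye. SAP 8.2 then says "The data imputation method will be applied to recurrence of uveitis in the fellow eye values in the same manner as the study eye". Its third rule is re-pointed to local drugs in the fellow eye.

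**What is permitted.** Protocol 9.7.1 says "The non-study eye may receive any local ocular treatment at the discretion of the investigator". SAP 8.1.2 acknowledges this: "although local medications are permitted in the fellow eye, in order to ensure consistency in analysis between the study eye and fellow eye", the study-eye list is treated as prohibited "for the fellow eye for the purposes of recurrence imputation".

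**Scope in the protocol.** Protocol 14.3.4.2 limits imputation to the primary outcome in the study eye. SAP 11.1 declares changes to the laboratory summaries, the recurrence definition and the handling of topical steroids. It does not declare the extension to the fellow eye.

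**The concern.** A recurrence needs a disease that can recur. SAP 8.1 also requires each criterion to be attributable to non-infectious uveitis. For a subject with unilateral disease who misses the Month 6 examination, the plan records a fellow-eye recurrence that meets no clinical criterion. For a subject with bilateral disease, a listed local drug given to the fellow eye within the protocol's own permission becomes an efficacy failure.

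The imputed events go beyond the proportion. SAP 8.2 includes recurrences imputed for missing data in the per-eye counts and sums recurrences over all study eyes and all fellow eyes. A subject with no earlier recurrence in either eye who misses Month 6 therefore adds two recurrences to the total, even in unilateral disease. The sensitivity analyses in SAP 8.1.3 and 8.2 concern the study eye only, so no planned analysis shows how much of the fellow-eye rate is imputed.

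**Working it through.** **1. The plan's own figure.** The only related figure is the 89% power for the study-eye comparison (SAP 4.1: recurrence-free rates 0.600 and 0.880, 40 and 80 subjects, continuity-corrected test). The continuity correction reduces the effective sham sample to 40 × [1 − 3/(2 × 2 × 40 × 0.28)]² = 34.82, and the power is then 0.892. The figure reproduces. The fellow-eye rule does not enter it.

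**2. Formula for the fellow eye.** The documents give no inputs, so all of these are assumptions: u, share with unilateral disease; m, share with a missing Month 6 examination; r, true recurrence in affected fellow eyes; l, listed local treatment in affected fellow eyes. Events are taken as independent.

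- True rate over all ITT subjects = (1 − u) r
- Reported rate = u m + (1 − u)[1 − (1 − r)(1 − m)(1 − l)]

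**3. Base illustration:** u = 0.40, m = 0.10, r = 0.20, l = 0.

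- True: 0.60 × 0.20 = 0.12
- Reported: 0.40 × 0.10 + 0.60 × (1 − 0.80 × 0.90) = 0.040 + 0.168 = 0.208, in both arms
- Excess: 0.208 − 0.120 = 0.088. Of this, 0.040 is in eyes with no uveitis and 0.60 × 0.80 × 0.10 = 0.048 is in affected eyes with a missing examination.
- In subjects, the 0.040 is 80 × 0.040 = 3.2 on FAI and 40 × 0.040 = 1.6 on sham.

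**4. Range with equal missingness**, r = 0.30 in both arms:

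| u | True rate | m | Reported, l = 0 | Reported, l = 0.20 |
|---|---|---|---|---|
| 0.30 | 0.21 | 0.05 | 0.250 | 0.343 |
| 0.30 | 0.21 | 0.10 | 0.289 | 0.377 |
| 0.50 | 0.15 | 0.05 | 0.193 | 0.259 |
| 0.50 | 0.15 | 0.10 | 0.235 | 0.298 |

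The l = 0.20 column is an upper illustration, because it treats local therapy as independent of true recurrence. Where the treated eye has already had a recorded recurrence, nothing is added.

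**5. Difference between arms.** With equal inputs it is zero. With unequal missingness it is (m sham − m FAI) × [u + (1 − u)(1 − r)(1 − l)].

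- Smallest case: 5% FAI, 10% sham, u = 0.30, l = 0.20: 0.05 × (0.30 + 0.70 × 0.70 × 0.80) = 0.035
- Largest case: 5% FAI, 15% sham, u = 0.50, l = 0: 0.10 × (0.50 + 0.50 × 0.70) = 0.085

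Missingness alone can thus produce 3.5 to 8.5 points where the true difference is zero, but only if it differs by arm. The documents do not say that it will.

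**The case against.** The choice is prespecified and the SAP gives a reason, consistency between eyes. The endpoint is exploratory and descriptive. The medication route is narrower than it first looks: topical steroids do not trigger imputation in the US/FDA analysis, systemic tapering is exempt, and only drugs judged able to affect the efficacy assessments are listed. What remains locally is mainly intra- or peri-ocular steroid, which Protocol 9.12 names among first-line treatments for a recurrence in either eye, so some of it will mark a real flare. Results are shown by eye, SAP 8.1.2 lists subjects with missing recurrence data, and the PP population excludes imputed endpoints. SAP 8.2 puts recurrences imputed for missing data into the counts and does not say the same of those imputed from medication.

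All of this stands, and it limits the size and reach of the problem. It does not remove it. Consistency between eyes is a weak reason, because only the study eye is randomized, must have uveitis and is denied local treatment. SAP 4.3.2 does not say whether a fellow-eye imputation alone removes a subject from PP.

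A reader might infer more: that systemic rescue for the study eye, expected more often on sham, also scores the fellow eye and so manufactures an apparent FAI benefit. With an assumed 15% systemic rescue on sham and 4% on FAI added to the base illustration, the rates would be 0.4 × 0.235 + 0.6 × 0.388 = 32.7% on sham and 0.4 × 0.136 + 0.6 × 0.309 = 24.0% on FAI. The documents do not support this as a finding. Protocol 9.10.2 excepts treatment of recurrences under Section 9.12, so such rescue is not clearly a prohibited drug. The gap comes wholly from the assumed 15% and 4%; without them both arms return to 20.8%. The text is nevertheless unclear: SAP 8.1.2 builds the list from drug coding terms for either eye and does not say that the reason for the drug is considered, although SAP 7.1.2 shows that the reason is recorded.

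**Conclusion.** The point holds as a defect in a descriptive endpoint. Followed as written, the SAP counts recurrences in fellow eyes that have no uveitis, may count permitted local treatment as recurrence, and departs from the protocol's study-eye-only imputation without declaring it. Under the base assumptions the fellow-eye rate is overstated by 8.8 points in both arms, 4.0 of them in unaffected eyes; other assumed inputs give more or less. A difference between arms depends on unequal missingness or listed medication use, which the documents neither state nor rule out. The fellow-eye proportion and the fellow-eye and total recurrence counts are affected. The primary test and its power are not. The textual part is certain. The size is illustrative, since every input to it is assumed.

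**What to change.** Amend SAP 8.1.2 and 8.2 as follows.

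- Report fellow-eye recurrence among subjects with a history of bilateral uveitis, already a variable in the imputation model of SAP 8.1.3 and Appendix 13.2. List any new-onset fellow-eye uveitis in unilateral subjects separately.
- Make observed recurrences that meet the criteria the main fellow-eye result. Show recurrences imputed for missing examinations in bilateral subjects on a separate line, so that a missing examination is not silently read as no recurrence.
- Do not impute from permitted local treatment of the fellow eye. No new table is needed, as SAP 8.2 already tabulates intra/peri-ocular and topical steroids by eye.
- State that systemic drugs given for the study eye do not by themselves create a fellow-eye recurrence.
- Apply the same rules to the per-eye and total recurrence counts.
- Declare the departure from Protocol 14.3.4.2 in SAP Section 11, under 11.1 or 11.2 according to whether it is made before or after unmasking.

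The cost is SAP wording and programming, with no new data. The downsides are a smaller denominator (with 40% unilateral disease, 0.60 × 80 = 48 FAI and 0.60 × 40 = 24 sham subjects) and a fellow-eye rule that no longer mirrors the study-eye rule.

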3.2. Study Endpoints

The primary efficacy endpoint is the proportion of subjects who have a recurrence of uveitis in the study eye within 6 months after receiving study treatment. Recurrence is captured on the Recurrence of Uveitis eCRF page and, for the US/FDA, is defined as:

- An increase in the vitreous haze of ≥ 2 steps, compared to baseline or any visit time point prior to Month 6
OR
- A deterioration in visual acuity of at least 15 letters BCVA, compared to baseline or any visit time point prior to Month 6

Any criterion used to define recurrence must be attributable only to noninfectious uveitis. To prevent post-procedural inflammatory reactions from being reported as uveitis recurrences, assessments for recurrence of uveitis begin after the study Day 7 visit.

The exploratory efficacy endpoints include:

- Proportion of subjects who have a recurrence of uveitis in the study eye within 12 months and 36 months
- Proportion of subjects who have a recurrence of uveitis in the fellow eye (within 6 months, 12 months and 36 months)
- Mean change from baseline in best-corrected visual acuity (BCVA) letter score in the study eye (at 6 months, 12 months and 36 months)
- Number of recurrences of uveitis (within 6 months, 12 months and 36 months)
- Time to recurrence of uveitis in the study eye (within 6 months, 12 months and 36 months)
- Number of adjunctive treatments required to treat recurrences of uveitis (within 6 months, 12 months and 36 months)
- Resolution of macular edema, as measure by OCT imaging (at 6 months, 12 months and 36 months)

In addition, the following safety endpoints will be included in the analysis:

- Systemic adverse events
- Ocular adverse events, including intra-ocular pressure (IOP) elevation
- Medications/procedures required to control elevated IOP
- Development or worsening of cataract
- Cataract-related procedures
- Clinically significant ocular changes
- Treatment related adverse events

4. General Statistical Considerations

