4.1. Sample Size

A two group continuity corrected Chi-square test with a 0.05 two-sided significance level will have 89% power to detect the difference between a Sham group recurrence free rate of 0.600 and a FAI treated group recurrence free rate of 0.880 (odds ratio of 0.205) when the sample sizes are 40 and 80, respectively (a total sample size of 120).

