4.2. Randomization, Stratification, and Masking

Subjects will be randomly assigned in a 2:1 ratio to either the FAI insert or sham injection through a central Interactive Voice Response System (IVRS). A blocked randomization will be used and randomization will be stratified on the basis of systemic treatment to control uveitis at the time of study entry. The three strata are: Not receiving systemic treatment, Receiving systemic treatment – corticosteroid therapy, and Receiving systemic treatment – immunosuppressive therapy. Stratification will be achieved dynamically through the IVRS.

To minimize bias, two investigators will be used at each study site. The unmasked treating investigator will inject the FAI insert or perform a sham injection and perform all assessments on study Day 1. The second investigator will serve as the masked assessing investigator and will perform all study assessments after Day 1. Only the unmasked treating investigator will know the assigned study treatment. Study personnel will use every reasonable effort to maintain the study mask.

Unmasking a subject's treatment to the assessing investigator should only be done in emergency situations for reasons of subject safety. In the event that an emergency unmasking is required, the assessing investigator/medically qualified designee has the authority to unmask a subject's treatment using IVRS, or its backup system if IVRS is not functioning. If possible, the assessing investigator/medically qualified designee should contact the PPD medical monitor or designee

before breaking the mask. When the masked treatment code is broken, the date and time of unmasking, name of person doing the unmasking, and the reason for unmasking must be fully documented in the source documentation. Treatment unmasking will also be recorded on the eCRF, including whether the FAI insert was removed and if so, the removal date. In the rare event that the FAI insert is removed, the subject should continue to be followed for safety and recurrence of uveitis through Month 36.

Randomization and unmasking data, for those subjects who were unmasked during the study, will be presented in a listing.

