8.1. Primary Efficacy Endpoint

[figure not shown]
The primary efficacy endpoint is defined as the proportion of subjects who have a recurrence of uveitis in the study eye within 6 months following treatment. As noted in section 4, all recurrence assessments (including unscheduled visits) on or before the upper limit of the 6 month visit window (Day 208) will be considered. Recurrence is captured on the Recurrence of Uveitis eCRF page and, for the US/FDA, is defined as:

- An increase in the vitreous haze of ≥ 2 steps ([Nussenblatt 1985](#)), compared to baseline or any visit time point prior to Month 6
OR
- A deterioration in visual acuity of at least 15 letters BCVA associated with recurrence of uveitis, compared to baseline or any visit time point prior to Month 6

Any criterion used to define recurrence must be attributable only to non-infectious uveitis. To prevent post-procedural inflammatory reactions from being reported as uveitis recurrences, assessments for recurrence of uveitis will begin after the study Day 7 visit.

The definition of a ≥ 2 step increase in vitreous haze is detailed in the diagram below.

Vitreous Haze: ≥ 2 step increase

* Nussenblatt et al 1985

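### The number-of-recurrences endpoint is reported as raw counts that mix observed with imputed events and ignore follow-up time, so its by-arm totals cannot be compared

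*SAP*

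**What the plan says.** SAP section 8.2 sets out the count: "For each subject and eye (study, fellow), the number of recurrences through Month 6, 12 and 36 will be calculated". It is shown with descriptive statistics and in categories from 0 to more than 5, and then "the total number of recurrences summed across all subjects, all study eyes and all fellow eyes will be presented by treatment group". The same paragraph says that recurrences imputed for missing data at Month 6, 12 or 36 count as recurrences here. Under SAP section 8.1.2, that imputation applies only to a subject with no earlier recurrence.

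A recurrence is defined in SAP section 8.1 by a change in vitreous haze or BCVA, "compared to baseline or any visit time point prior to Month 6". The BCVA criterion must be associated with recurrence of uveitis, and every criterion must be attributable only to non-infectious uveitis. Events are taken from a dedicated eCRF page. Protocol section 9.12 asks for each recurrence and its treatment to be documented, and it speaks of a recurrence being controlled without defining that state.

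SAP section 7.3.1 summarises duration of participation, but nothing links it to the recurrence count. On allocation, SAP section 4.2 states: "Subjects will be randomly assigned in a 2:1 ratio to either the FAI insert or sham injection".

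**The concern.** A count over 36 months is informative only if the reader knows how long each eye was examined and what separates one event from the next. The plan supplies neither. Its raw totals combine four things: how often eyes recur, how long subjects stay, how many subjects are in each arm, and how many events were assigned because data were missing. A difference in totals between FAI and sham could come from any of them.

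The lack of an episode rule adds to this. A definition that compares with any early visit works for a yes/no endpoint. When it is used to count, an eye that stays worse can still meet the numeric threshold at later visits. The number recorded then depends on site practice that neither document describes.

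Timing matters as well. Under SAP section 4.2.1 the sponsor and the biostatistics and programming teams are unmasked after the Month 6 lock. Any counting rule chosen later for Months 12 and 36 would be chosen with knowledge of treatment.

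**Working it through.** **The plan's own figure.** The only design calculation concerns the primary comparison: "A two group continuity corrected Chi-square test with a 0.05 two-sided significance level will have 89% power", for a "Sham group recurrence free rate of 0.600 and a FAI treated group recurrence free rate of 0.880", with 40 sham and 80 FAI subjects.
- Pooled rate = (40×0.60 + 80×0.88)/120 = 0.7867.
- Null SE = √(0.7867×0.2133×(1/40+1/80)) = 0.0793.
- Alternative SE = √(0.24/40 + 0.1056/80) = 0.0856.
- Continuity correction = 0.5×(1/40+1/80) = 0.01875.
- z = (0.28 − 0.01875 − 1.96×0.0793)/0.0856 = 1.236, so power = 0.892.

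The stated 89% reproduces. It has no bearing on the count, for which no figure is given.

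**Step 1: allocation.** If the mean count per study eye is m in both arms, the expected totals are 80m (FAI) and 40m (sham). That is a ratio of 2 with no treatment difference.

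**Step 2: follow-up and imputation.** Assume, for illustration, a constant Poisson rate of r recurrences per year, and compare the counts through Month 36.
- Completer: expected count 3r.
- Subject leaving at Month 6: 0.5r observed, plus one imputed event if none occurred, which has probability e^(−0.5r).

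| r per year | Completer, 3r | Drop-out, observed | Drop-out, imputed | Drop-out, total |
|---|---|---|---|---|
| 0.5 | 1.5 | 0.25 | 0.78 | 1.03 |
| 1 | 3 | 0.50 | 0.61 | 1.11 |
| 2 | 6 | 1.00 | 0.37 | 1.37 |

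At these rates the drop-out is under-counted. As r approaches 0, the completer's count tends to 0 and the drop-out's to 1, so the bias reverses. The two are about equal near r = 0.34: 3×0.34 = 1.02, against 0.17 + e^(−0.17) = 1.01. At r = 0.5, about three-quarters of the drop-out's count (0.78/1.03) is imputed.

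A rate based on observed events removes this under the same assumption: 0.5r/0.5 = r for the drop-out and 3r/3 = r for the completer.

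**Step 3: repeated recording.** Recurrence is assessed after the Day 7 visit. The later scheduled visits are Day 28 and Months 2, 3, 6, 9, 12, 18, 24, 30 and 36. That makes 4 visits to Month 6, 6 to Month 12 and 10 to Month 36. A flare present from Day 28 onward is one recurrence if episodes are counted. If every qualifying scheduled visit were recorded, it could be up to 4, 6 or 10. Unscheduled visits, which SAP section 4 also admits, could add more. This is the range the wording permits, not an expected value.

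**Step 4: comparison with neighbouring text.** For adjunctive treatments, also in SAP section 8.2, repeated doses within one regimen count as one treatment. For ocular adverse events, SAP section 9.1.1 compares haze with the last examination, which marks an onset. The recurrence count has neither device.

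**The case against.** The endpoint is exploratory and descriptive. The primary analysis, its sensitivity analyses and time to first recurrence need only a first event. Per-subject distributions are given beside the totals, so a reader can allow for arm size, and duration of participation is tabulated. The per-protocol set in SAP section 4.3.2 removes subjects with imputed endpoints, which gives a partial view without them. All of this stands and keeps the point modest. It does not remove it. The per-subject summaries still ignore follow-up time. The per-protocol set keeps a subject who recurred and then left, because that subject is not imputed for missing data.

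Several stronger readings are tempting, and the documents do not support them:
- A reader might infer that a lasting flare counts at every visit. The SAP does not say that each qualifying visit is a new recurrence. Events come from an eCRF page that cannot be seen here, and the protocol treats recurrences as discrete, treated events.
- A reader might infer that a permanent vision loss keeps counting. The loss must be associated with recurrence of uveitis, so a fixed deficit in a quiet eye does not plainly qualify again.
- A reader might infer that a drop-out collects imputed events at Months 6, 12 and 36 in turn. The natural reading of SAP section 8.1.2 is one imputation per analysis, limited to subjects without an earlier recurrence.
- A reader might infer that drop-outs are always under-counted, or that sham is always inflated. Step 2 shows that the direction varies, and nothing in the documents fixes it by arm.

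**Conclusion.** The point holds as a limited one about an exploratory summary. Two facts can be read directly from the text: imputed and observed recurrences are pooled, and no follow-up time is used. Raw totals differ twofold under equal frequencies because of allocation alone. A Month 6 drop-out's count through Month 36 falls well short of a completer's at 0.5 to 2 recurrences per year (1.03 against 1.5, up to 1.37 against 6). It exceeds the completer's below roughly 0.34 per year. Those figures rest on an assumed constant Poisson rate and exit at Month 6; the documents give neither a recurrence rate nor a drop-out rate.

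The missing end-of-recurrence rule is a gap that permits repeated recording. It is not evidence that repeated recording will happen.

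**What to change.** For this endpoint, report observed recurrences per subject-year of examined follow-up, by arm and separately for study and fellow eyes. Give a 95% confidence interval that allows for over-dispersion, for example from a negative binomial model or a Poisson model with robust standard errors. Show imputed recurrences on a separate line, at most one per eye.

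Count distinct recurrences that the investigator has attributed to uveitis, as recorded on the Recurrence of Uveitis eCRF page. Do not re-derive them from haze and BCVA values alone, since that would lose the attribution. The sponsor should set the rule for when a new recurrence may be counted and apply it to the haze and BCVA criteria separately. Otherwise a lasting vision loss would block every later haze flare in that eye.

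If the change is made after the Month 6 lock, record it in SAP section 11.2, which already lists clarifications made after unmasking.

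The cost is SAP wording and a little more analysis, and some closely spaced flares may be merged. A rate also does not correct for drop-out that is related to disease activity, so participation by arm should be shown beside it.
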